Consumption of gases (Oxygen, Air and Sevoflurane) from the beginning until T₁₅ will be retrieved. Any reduction in mean BP >20% from the baseline will be treated with intravenous Ephedrine 12 mg bolus and consumption of Ephedrine will be noted. Expired minute volume (MV_E) at T_{target} and T₁₅ will be noted. The study period will end at T₁₅ in both the groups. Painting the surgical parts and draping will be permitted during the study period. Care will be taken to avoid any activity which risks ETT disconnection during the study period. Subsequent management of anaesthesia will be left to the discretion of the attending Anaesthesiologist.

For both the groups, 'stability of Sevoflurane concentration', defined as FAS in the target range of 1.6-2.4% during the time interval from T_{target} till T₁₅ will be assessed. The investigator will be allowed during this period to increase or decrease if needed the vapouriser dial by 1% at a time every 2 min to keep the FAS in the target range. The number of times the vapouriser dial is adjusted will be noted. The system will be considered 'stable' if the FAS is maintained in the target range without the need for dial adjustment and 'unstable' if vapouriser dial adjustment is needed at any time during this period.

Delivery of Oxygen will be monitored to ensure at least 300 ml/min and delivered F_1O_2 at least 0.3 at all time. The investigator will be allowed to increase if needed the set F_1O_2 by 0.1 at a time every 2 min to keep the delivered $F_1O_2>0.3$. The number of times the set F_1O_2 is adjusted will be noted. End-tidal carbon dioxide (ETCO₂) will be maintained between 30 and 40.

The aim of the study is to assess during the wash-in phase of LFA the feasibility of the method, stability of the system and consumption of gases. The primary outcome will be the time required to achieve FAS 2%. Secondary outcomes will be the stability of the system assessed by the number of times vapouriser dial and the set F1O₂ adjusted, consumption of gases and of ephedrine.

Statistical analysis

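### The dial-stability window is 15 minutes minus the primary outcome, so a raw comparison favours whichever arm reaches FAS 2% later

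*Protocol*

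**What the plan says.** All the relevant definitions are in the protocol's Methods section.

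- T_target is the time from opening the vapouriser to FAS 2%. It is also the primary outcome.
- Stability is "defined as FAS in the target range of 1.6-2.4% during the time interval from T_{target} till T₁₅ will be assessed".
- The end of the window is common to both arms: "The study period will end at T₁₅ in both the groups".
- The favourable label is given when "the FAS is maintained in the target range without the need for dial adjustment". A patient's system gets the opposite label "if vapouriser dial adjustment is needed at any time during this period".
- During the window the investigator may "increase or decrease if needed the vapouriser dial by 1% at a time every 2 min to keep the FAS in the target range". For these changes, "The number of times the vapouriser dial is adjusted will be noted"; their times are not mentioned.
- The aim covers "the feasibility of the method, stability of the system and consumption of gases". The outcome list reads "Secondary outcomes will be the stability of the system assessed by the number of times vapouriser dial", together with the set-F1O2 adjustments.

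The Statistical analysis section names Student's t, Kruskal-Wallis, chi-squared and Fisher tests. It assumes about 8 min for Group OP and sizes the trial for a 2-min difference with SD 2. It states neither the direction of that difference nor an expected time for Group C.

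**The concern.** A count of events, or a label that asks whether any event occurred, tends to rise with the time observed. Here that time is set by the primary outcome, which the trial is sized to find different between arms.

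If Group OP is slower, the new method can look as stable as the conventional one, or more so, because it was watched for less time. If Group OP is faster, it is penalised for doing well on the primary outcome. Either way, part of the stability result restates T_target: equal stability per minute can look like a difference, and a real disadvantage of the later arm can be hidden. Stability is one of the study's stated aims, and the dial count is how it is measured.

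**Working it through.** **Inputs from the protocol.** Window from T_target to 15 min; at least 2 min between dial changes; T_target about 8 min in Group OP; difference 2 min; SD 2; 24 per arm. The protocol gives no adjustment rate, so 0.05, 0.1 and 0.2 per minute are assumptions.

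**The plan's own figure.** n per arm = 2(1.960 + 1.282)² × 2²/2² = 21.01, which rounds up to 22. The stated 22 reproduces as a two-sided calculation, so the trial has 90% power to find the 2-min difference that makes the windows unequal.

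**Window length** = 15 − T_target.
- T_target 6 min: 9 min
- T_target 8 min: 7 min
- T_target 10 min: 5 min

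**Expected counts.** At a constant rate r the expected count is r × window, ignoring the 2-min spacing. The earlier arm therefore expects 9/7 = 1.29 times (C at 6, OP at 8) or 7/5 = 1.40 times (C at 10, OP at 8) as many adjustments. Equivalently, raw counts look equal when the later arm's true rate is 29% or 40% higher.

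**Label.** P(stable) = exp(−r × window). At r = 0.1 this is 0.41, 0.50 and 0.61 for T_target of 6, 8 and 10 min.

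**False positives when both arms share the same rate.** Simulation with 24 per arm, T_target normal with SD 2 (truncated to 0.5–14.5 min), 2-min spacing and 10,000 trials per cell:

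| Mean T_target, C v OP (min) | Mean count at 0.1/min | Unstable at 0.1/min | Rank test on counts at 0.05/0.1/0.2 | Fisher on label at 0.05/0.1/0.2 |
|---|---|---|---|---|
| 6 v 8 | 0.77 v 0.60 | 59% v 49% | 8/12/19% | 4/6/7% |
| 8 v 8 | 0.60 v 0.60 | 49% v 49% | 5% | 3% |
| 10 v 8 | 0.44 v 0.60 | 39% v 49% | 9/13/21% | 5/8/9% |

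At a 1-min difference the figures are 6–9% (rank) and 3–4% (Fisher). A separate simulation of a t-test on raw counts (22 per arm, no spacing rule) gave 7.7–16.6% for 6 v 8 and 8.3–19.8% for 8 v 10. Nearly all of these rejections favoured the later arm.

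**If the rate is not constant** (2-min difference):
- Adjustments clustered early: rank 6–11%, Fisher 3–4%.
- Adjustments coming late: rank 15–37%, Fisher 9–24%.
- FAS drifting from 2.0% and corrected by the dial: rank 16–20% and Fisher 5–9% for 6 v 8; rank 18–28% and Fisher 11–13% for 10 v 8; rank 4–5% and Fisher about 3% for 8 v 8. This model assumes patient drift SD 0.05 or 0.10% per min and a dial change at 0.3 or 0.4 from 2.0. Each 1% step shifts drift by 0.5 L/min × 1% / 9.5 L = 0.053% per min, using the midpoint of the 9–10 L reserve volume in the Introduction.

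**The alternatives in the same settings.**
- Log-rank on time from T_target to the first of dial adjustment or out-of-range FAS: 4.6–7.2% under drift, 4.4–6.7% across rate shapes.
- Count model with log window as offset and dispersion adjustment: 3–5% at a constant rate, 3–13% with early or late adjustments, 5–10% under drift. Plain Poisson gives 6–17% under drift.
- FAS readings alone: among patients who needed an adjustment, 50–83% (dial changed at 0.3) or 15–36% (at 0.4) never had an out-of-range reading, so they would be called stable.

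**The case against.** **The effect is modest.** On the protocol's own stable/unstable label, Fisher's test at the planned difference rejects in only 4–9% of trials at a constant rate. This stands, and it limits the severity. It does not cover the count, which is the listed secondary outcome.

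**The direction and the difference are conditional.** The 2 min is a difference to detect, not a forecast. The nearest cited regimen to Group C (6 L/min, 2.5% dial) took 8.2 min, which against 8 min implies almost no bias. That study used nitrous oxide and a different dial setting, and its endpoint was a ratio that the Introduction equates with FAS 2%, so it anchors Group C's time only loosely. The condition stands: no difference in T_target, no bias.

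**The raw count may be what is wanted.** Both arms are followed for the same 15 min, and the Introduction stresses simplicity during a busy phase. Total dial changes are a fair measure of workload. The protocol, however, calls the measure stability and defines it from T_target onwards, so the workload reading does not support a stability conclusion.

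**An analysis plan could supply a rate or a time-to-event method.** It could. But the window, the count and the label are already fixed in the protocol, and followed as written they favour the later arm.

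**The simplest remedy is imperfect.** This is correct: the offset model is reliable only if the rate is roughly constant.

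**Conclusion.** The concern holds and should be fixed. The stability window is exactly 15 min minus the primary outcome, and neither the count nor the label allows for that. At the planned 2-min difference and a constant, equal rate, the false-positive rate is 8–21% for a rank test on counts and 4–9% for Fisher's test on the label. The size depends on assumed adjustment rates, on how adjustments are spread over the window, and on T_target actually differing between arms; which arm would benefit cannot be told from the protocol. The set-F1O2 count does not start at T_target and is not affected, nor are the primary outcome, sample size or gas consumption.

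**What to change.** Keep the protocol's definition of instability, and compare it on equal exposure.

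1. Report dial adjustments per minute of window, using a count model with log(15 − T_target) as offset and a dispersion-adjusted standard error. State that it assumes a roughly constant rate. This is wording only, since T_target and the number of adjustments are already recorded.
2. Preferably, also record the time of each dial change. Compare time from T_target to the first of dial adjustment or FAS outside 1.6–2.4%, censored at T15, by log-rank. This costs one time stamp per change. FAS is noted only once a minute after T5, so the timing of excursions will be coarse.
3. Treat time to out-of-range FAS alone as supportive, because a dial change can prevent the excursion.
4. Raw counts to T15 may be described as workload, with window length beside them. No between-arm stability conclusion should rest on them alone.

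An equal fixed window after T_target is possible but loses patients. A 5-min window is incomplete when T_target exceeds 10 min, which is 16% of an arm at 8 ± 2 min and 50% at 10 ± 2 min.

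The price is that any apparent stability advantage of the later arm may shrink, and that item 1 on its own gives incomplete protection if adjustments are not spread evenly.

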In a test lung model study Jakobsson et. al.4 reported wash-in with a respective FGF of 0.3 and 4 L·min-1 and a FvS of 8%. They found that the FaS reached 1 MAC (2.1%) at 547 ± 83 and 38 ± 6 s, respectively. It was possible to increase the AA concentration from 0 to 1 MAC value in around one minute by using a FGF of 4–4.8 L/min using a fixed dial setting of 3 MAC, but raising the FGF further did not result in shorter wash-in times. Wash-in times were significantly faster with higher flow rates for FGF spanning from 1, 2 and 4 L/min, however a plateau started at FGF 4–4.8 L/min, where increasing the FGF further up to 6 or 8 L/min did not shorten the time to reach 1 MAC significantly.¹³

The conventional method which uses initial high FGF during the wash-in phase defeats the purpose of LFA such as conservation of gases, reduced environmental pollution and economical savings even

though it provides a more stable gas composition within the breathing system. Beginning of anaesthesia is also a task-intense phase requiring multiple tasks to be performed to ensure the patient safety. Any additional tasks during this phase may have high chances of being forgotten with a potential for compromised patient safety. Therefore, the technique has to be simple to execute. We wish to evaluate a technique of initiating Sevoflurane LFA which is simple, has a quick wash-in and minimises gas consumption without compromising the safety when compared to conventional method of attaining LFA using initial high flows.

Methods

After obtaining the approval from the Institutional Ethics Committee of The Royal Hospital, Muscat, we will register this prospective, randomised, descriptive study in an appropriate online clinical trial registry. A written informed consent will be obtained from all the patients. Forty-eight patients of either gender aged 18-65 years, with American Society of Anesthesiologists (ASA) physical status of 1-2, undergoing elective surgery with the expected duration more than 1 hour under general anaesthesia requiring endotracheal intubation will be included. Pregnant women, smokers, patients with a body mass index (BMI) \geq 30 kg/m₂, cardiac/pulmonary/renal or liver impairments, upper or lower respiratory infections within the past 6 weeks and anticipated difficult airway will be excluded.

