Sample size is calculated based on a previous study₈ which showed the 1-1-8 wash-in scheme with FGF=2L (O₂ 1 L + Air 1 L) and Sevoflurane dial at 8% yielded an F_AS of 2% at 2 ± 0.5 min. Hence, we assume that with our wash-in technique using FGF=0.5 L (O₂ + Air) and FvS 8% the time needed to reach F_AS=2% will be around 8 min. To detect a difference of 2 min (25%) with standard deviation (SD) of 2 using an alpha level of 0.05 and a power of 0.90 the sample size needed is 22 per group. For a possible 10% dropouts, it is decided to include 24 patients per group.

Statistical analysis will be carried out using an appropriate statistical software. Data will be presented as mean \pm SD or median (range). Intergroup differences will be assessed for significance using Student's t, Kruskal-Wallis, chi-squared or Fisher exact tests, as appropriate. P < 0.05 will be considered statistically significant.

Study duration: Approximately 8 months (from December 2023 to July 2024). Data collection: December 2023-May 2024, statistical analysis and writing manuscript: June-July 2024.

How will the expenses be met with? : Does not involve any additional expenditure.

Department associated in the study: Department of Anaesthesia and Intensive Care, Royal Hospital, Muscat.

References

1. Baum JA. Low-flow anesthesia: theory, practice, technical preconditions, advantages, and foreign gas accumulation. J Anesth. 1999;13(3):166-74. doi: 10.1007/s005400050050. PMID: 14530937.

4. Jakobsson P, Lindgren M, Jakobsson JG. Wash-in and wash-out of sevoflurane in a test-lung model:
A comparison between Aisys and FLOW-i. F1000Res. 2017 Mar 29;6:389. doi: 10.12688/f1000research.11255.2. PMID: 28529707; PMCID: PMC5414818.

5. Feldman JM. Managing fresh gas flow to reduce environmental contamination. Anesth Analg. 2012 May;114(5):1093-101. doi: 10.1213/ANE.0b013e31824eee0d. Epub 2012 Mar 13. PMID: 22415533.

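### Does the primary comparison need a limit on acceptable delay, because a P < 0.05 test cannot say whether the over-pressure wash-in is quick enough?

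*Protocol*

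**What the plan says.** The Introduction closes by saying that the investigators want a technique "which is simple, has a quick wash-in and minimises gas consumption without compromising the safety when compared to conventional method of attaining LFA". Under Methods, the aim is put more modestly: "The aim of the study is to assess during the wash-in phase of LFA the feasibility of the method", together with stability of the system and gas consumption. The same section fixes the endpoint: "The primary outcome will be the time required to achieve FAS 2" per cent. Both the title and Methods call the study descriptive.

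The Statistical analysis section starts from an earlier scheme run at 2 L/min and assumes that for the over-pressure method "the time needed to reach F_AS=2% will be around 8 min". The planning sentence follows: "To detect a difference of 2 min (25%) with standard deviation (SD) of 2 using an alpha level of 0.05". With power 0.90 this gives 22 per group, raised to 24 for dropouts. Data are to be summarised as mean ± SD or median (range), and groups compared with standard tests of difference. The only inferential criterion is "P < 0.05 will be considered statistically significant".

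**The concern.** The over-pressure method is expected to gain on gas use and simplicity, so its speed looks like something to be shown tolerable rather than superior. A test of difference answers that only if Group OP is significantly faster. A significantly slower result does not say whether the delay is acceptable, and a non-significant result does not show similar speed.

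The planning text adds to the doubt. Since 2 min is 25% of 8 min, the Group C mean could be 6 or 10 min, and the section does not say which. Methods sets numerical limits for stability and oxygen delivery but none for wash-in time. If this were a real fault, the 90% power would attach to a question nobody is asking, and the judgement of what counts as quick would be made after the data were seen.

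**Working it through.** **Inputs (Protocol, Statistical analysis).** Difference 2 min, SD 2 min, alpha 0.05, power 0.90, 22 per group before dropouts. Sidedness is not stated.

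**1. Reproduce the sample size.** n per group = 2(z₀.₉₇₅ + z₀.₉₀)²(SD/difference)² = 2(1.960 + 1.2816)²(2/2)² = 21.01, rounded up to 22. A one-sided 0.05 test would give 17.1, so the stated figure is that of a two-sided test. Exact t-test power is 0.8997 at 22 and 0.924 at 24 per group. The formula uses only the difference and the SD. The Group C mean and the sign of the difference do not enter it.

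**2. What the test decides.** Standard error at 22 per group = 2 × √(2/22) = 0.603 min. The 95% half-width = 2.018 × 0.603 = 1.217 min. At 24 per group it is 2.013 × 0.577 = 1.162 min. So an observed gap of about 1.22 min in either direction is already significant. The 2 min is the planning effect, not the threshold for a decision.

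**3. Where the test alone is silent (illustrative values, not from the Protocol).**

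| Observed OP minus C | t | P | 95% CI (min) |
|---|---|---|---|
| +1.1 min | 1.82 | 0.075 | −0.12 to 2.32 |
| +1.5 min | 2.49 | 0.017 | 0.28 to 2.72 |

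The first is not significant but allows a delay above 2 min. The second is significant but says nothing of acceptability. If Group OP is truly 1 min slower, power is 0.367, so about 63% of such trials end with P ≥ 0.05. In each row the interval gives the information that the P value lacks, and it comes from the same means, SDs and group sizes as the planned test.

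**4. What the Protocol's background suggests.** The Introduction cites 8.2 ± 2.1 min at 6 L with the dial at 2.5% and nitrous oxide, and describes conventional high flow lasting about 3 min. Neither matches Group C exactly, and the sample-size text adopts neither. Against the assumed 8 min they imply OP minus C of 8 − 8.2 = −0.2 min, or 8 − 3 = +5 min. These are near-equality or a large delay. The in-between delays in step 3 are not what the documents lead one to expect.

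**5. What a limit would do at the planned size.** The documents give no limit. Taking 2 min purely for illustration, success needs an observed delay below 2 − 1.217 = 0.78 min.

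| True OP delay | Chance that the upper CI limit is below 2 min (22 per group) | n per group for 90% |
|---|---|---|
| 0 | 0.900 | 22 |
| 0.5 min | 0.681 | about 39 |
| 1 min | 0.367 | about 85 |

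By the normal formula, a 3-min limit with a true delay of 1 min again needs 22 per group. The answer therefore depends on a limit that only the sponsor could choose.

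**The case for a change.** The strongest case for a change is that the trial has a powered between-group primary test, so calling it descriptive does not excuse the lack of a stated hypothesis. The type of hypothesis and any margin determine sample size and so belong in the protocol, not in a later analysis plan. The background figures point to no difference or to a slower Group OP, the two results that a test of difference interprets least well. Reporting an interval and naming a limit would need no extra patients.

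Part of this stands. The assumed Group C time and the reason why 2 min matters are absent, and the difference with its interval would be the more informative primary result.

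The rest does not carry. The requirement that Group OP be acceptably quick within some bound is not in the Protocol. In the Introduction's sentence, the comparison with the conventional method follows directly on the safety clause; extending it to speed is one reading of loose wording. A method that is slower but uses less gas is a legitimate finding for a feasibility study. Nothing in the text says that P ≥ 0.05 will be taken as equal speed, so a disclaimer would correct no stated error. A limit set late would also protect little: the Protocol describes no blinding, and staff change flow or dial when the 2% target is reached, so they see each time as it occurs.

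**Conclusion.** The concern does not call for a change. The Protocol specifies a valid two-sided comparison, and its 22 per group at 90% power is correct for the stated difference and SD. Followed as written, no number or rule gives a wrong result.

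The missing Group C time and the reason for 2 min are gaps in explanation. They bear on how well chosen 2 min is, not on the calculation. The confidence interval is ordinary reporting that an analyst would supply and that an analysis plan, not at hand here, may already contain. A limit on acceptable delay is a design option with a real trade-off: at the planned size, the illustrative 2-min limit has a 90% chance of being met only if there is no true delay, 68% at 0.5 min and 37% at 1 min.

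These figures assume the Protocol's SD of 2 min in both groups, roughly normal times and 22 analysed patients per group. With an SD of 3 min the half-width would be 1.217 × 3/2 = 1.83 min. If times prove skewed and are summarised as median (range), the interval must come from the patient data rather than the published summaries. The analysts will hold those data.

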Volatile anaesthetic agents are unique in that it is possible to significantly reduce the mass of drug delivered to the circuit (by lowering FGFs) without altering the amount that actually enters the patient.⁶ Studies have shown that 1 L/min change in FGF with Sevoflurane results in a change of between 4 and 18 ml/hour consumption of sevoflurane.⁷ The challenge is to control the dynamic equilibrium of FG composition as the uptake and metabolism are time-sensitive and many factors influence the consumption and production of gaseous components. This can be achieved only through frequent adjustments in the gas flow controls.¹

LFA requires flow meters calibrated to low flow down to 50 ml/min, leak-proof circle breathing system and airway devices like cuffed endotracheal tube (ETT), gas monitoring system providing inspired and end-tidal concentrations of agent, vapourisers capable of delivering high concentrations and calibrated to be accurate at low FGF. Since low FGFs are added to significantly large reserve volume (approximately 9-10 litres), consisting of breathing tubing, reservoir bag, anaesthetic ventilator, intergranular space, etc., in addition to functional residual capacity (FRC) of the patient, it requires 3time constants (calculated by reserve volume divided by FGF) to effect 95% change in gas composition to occur. However, once steady state is achieved, LFA provides the most economic use of anaesthetic agents. Sevoflurane when used with strong base-free CO₂ absorbent is suitable for use in LFA because it has low blood-gas solubility. The minimum alveolar concentration (MAC) of Sevoflurane varies with patient age, from 1.4% at age 80 years to 2.3% at age 1 year.8 The optimal alveolar concentration of Sevoflurane (FAS) to prevent motor movement and autonomic response during anaesthesia is MAC-Bar which approximates 1.5 MAC. Thus, the target of FAS during anaesthesia in daily practice varies between 1 to 3.5%, depending on the adjuvant drugs used.

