Since use of low FGF leads to a long time constant, a wash-in phase using a high FGF and high vapouriser concentration (Fv) of volatile anaesthetic is warranted in order to rapidly achieve the required concentration of inhalation anaesthetic in the breathing system.⁸ Conventionally LFA is administered using high flows initially up to 4-10 L/min for 3-time constants (approximately 3 minutes) with Sevoflurane dial setting of 0.8-2.5% to bring the circuit to the desired concentration, then the flows are reduced for maintenance of anaesthesia. In this method of initial high flows, there is risk of delivering high anaesthetic concentrations during induction of anaesthesia and wastage of volatile agents when the total consumption of anaesthetic agent (AA) is calculated at the end of surgery.

Wash-in is the time taken to reach 1 MAC concentration. Sevoflurane wash-in schemes lack simplicity, target coverage and applicability. Various studies have demonstrated that the time to reach 1 MAC decreased at higher flow rates (1-2-4) but plateaued at 4-4.8 L/min. Lindqvist et. al.9 reported a 2-step wash-in technique to achieve a FAS of 1.2%; starting with FGF 1 L·min-1 and FvS 8% for 1 min, then reducing FGF to 1, 0.7, 0.5, and 0.3 L \cdot min-1. They found that the respective time to achieve the target FAS was 1.8, 1.5, 2.5 and 3.6 min. Horwitz et. al.10 reported that by using a FGF of 1.0 or 0.5 L·min-1 with a FvS 6% during the wash-in, the respective time to reach 1 MAC was 6.2 ± 1.3 and 15.2 ± 2.4 min and up to 1.5 MAC at 7.5 ± 2.5 and 19 ± 4.4 min. Shin et al.11 performed a wash-in study using a Primus anaesthetic machine connected to a test-lung, using a FGF of 0.5, 1, and 3 L·min-1 and setting the FvS to 6%. The respective mean time to reach a FAS of 4% for each FGF was 1165, 534, and 155 s. Nel MR et. al. 1_2 have shown while using FGF=6 L (Nitrous Oxide 4L + O₂ 2L) and Sevoflurane vapouriser dial set at 2.5% that equilibration point defined as FE/FI=0.8 (corresponding to FAS=2%) can be reached in a mean (standard deviation) of 8.2 ± 2.1 min. Tribuddharat S et. al.8 studied the 1-1-8 wash-in scheme with FGF=2L (O₂ 1 L + Air 1 L) and FvS 8% which yielded a respective FaS of 1, 1.5, 2, 2.5, 3, and 3.5% at 1, 1.5, 2, 3, 3.5, and 4.5 min when used with N2O and at 1, 1.5, 2, 3, 4, and 5 min when used with air.

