Heart rate (HR), blood pressure (BP) and peripheral oxygen saturation will be recorded before induction of anaesthesia, every minute until 5 min after induction and every 5 min intervals thereafter. The FGF will be set at 6 L/min with 100% O₂ during pre-oxygenation and manual ventilation. Following pre-oxygenation for 3 min, general anaesthesia will be induced with intravenous Fentanyl 2 μ g/kg followed by Propofol 2 mg/kg administered over 30 seconds and Rocuronium 1 mg/kg for neuromuscular blockade. Lungs will be ventilated manually and propofol 20 mg every minute will be administered until tracheal intubation. Tracheal intubation with an appropriate size ETT will be performed 90 seconds later, the cuff inflated to 25-30 cmH₂O using a cuff-pressure monitor device and ETT secured with an adhesive tape. The correct ETT position will be confirmed by auscultation and square-wave capnograph. FGF will be paused during intubation and restarted after inflating the ETT cuff. The FGF hereafter will consist of O₂ and Air with a set F₁O₂=0.6. FGF and Sevoflurane vapouriser dial (FvS) will be set as per the group allocation and mechanical ventilation will begin. The time of opening of vapouriser will be considered T_{zero}.

Following will be the steps during wash-in for achieving LFA:

The 'conventional' group (Group C): FGF will be set to 6 L/min and the FvS 3% at T_{zero}. The FGF will be reduced to 0.5 L/min upon reaching FaS 2%. Hereafter, the FvS will be set to 4% and maintained till 15 min (T₁₅) from T_{zero}.

The 'over-pressure' group (Group OP): FGF will be set to 0.5 L/min and FvS 8% at Tzero. Subsequently, the FvS will be set to 4% upon reaching FAS 2% and maintained till 15 min (T15) from Tzero.

The time of reaching $F_AS=2\%$ will be noted in both the groups. The time taken in seconds from T_{zero} to reach $F_AS 2\%$ (T_{target}) will be calculated. Inspired concentration of Sevoflurane (FiS), FaS, and age-adjusted MAC will be retrieved from the automatically recorded 'trend' of parameters. FiS, FaS and age-adjusted MAC will be noted every 30 sec. starting from T_{zero} , till T_5 and every minute thereafter until T₁₅.

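### Does the sample size fail because the 2-minute difference comes with no expected wash-in time for Group C?

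*Protocol*

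**What the plan says.** In the Statistical analysis section, the protocol starts from an earlier study at 2 L/min and an 8% dial, which reached the target in 2 ± 0.5 min. For its own over-pressure technique (0.5 L/min, 8%) it then assumes that "the time needed to reach F_AS=2% will be around 8 min". The next sentence sets the size of the trial: "To detect a difference of 2 min (25%) with standard deviation (SD) of 2 using an alpha level of 0.05" and power 0.90, hence 22 per group, raised to 24 for dropout. The endpoint is fixed at the end of Methods: "The primary outcome will be the time required to achieve FAS 2"%.

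Group C starts at 6 L/min with a 3% dial (Methods, wash-in steps). No expected time is attached to those settings anywhere.

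The Introduction contains two high-flow figures that a reader might borrow. One describes conventional practice as "high flows initially up to 4-10 L/min for 3-time constants (approximately 3 minutes) with Sevoflurane dial setting of 0.8-2.5"%. The other comes from a study at 6 L/min with nitrous oxide and a 2.5% dial, where an equilibration point "can be reached in a mean (standard deviation) of 8.2 ± 2.1 min". Neither is cited in the sample-size paragraph.

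**The concern.** A two-arm comparison appears to be sized from one arm. Since 2/8 = 25%, the percentage refers to the over-pressure arm's own assumed time. Read as an expected contrast, 2 min puts Group C at 8 − 2 = 6 min or 8 + 2 = 10 min, and neither value is stated or sourced. Read instead as the smallest difference that matters, it lacks a reason.

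The Introduction seems to make this worse. Set against 8 min, the 8.2 min figure leaves almost no contrast and the 3-minute figure leaves about 5 min. If those were fair forecasts for Group C, the primary comparison would be either nearly hopeless or a foregone conclusion, and the stated 90% would describe neither case.

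**Working it through.** **The plan's own figure.** Inputs from the Statistical analysis section: difference 2 min, SD 2 min, alpha 0.05, power 0.90. Sidedness is not stated; two-sided is taken because it reproduces the result (one-sided gives 18).

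- n per group = 2 × (1.95996 + 1.28155)² × (2/2)² = 2 × 10.507 = 21.01, rounded up to 22.
- t-test power at 22 per group = 0.900.

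The Group C mean does not enter this formula, and for a two-sided test neither does the direction. The stated power refers to a 2 min difference with SD 2.

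**The two borrowed figures, taken at face value** (over-pressure arm 8 min, SD 2, 22 per group, two-sided t-test):

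| Assumed Group C time | Difference (OP − C) | Power |
|---|---|---|
| 8.2 min | −0.2 min | 0.062 |
| 6 min (implied by the plan) | 2 min | 0.900 |
| 3 min | 5 min | above 0.999 |

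**Do those figures measure Group C's primary outcome?**

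- *Three minutes.* This is how long high flow is run, at dials from 0.8% to 2.5%. A dial below 2% cannot bring the end-tidal concentration up to 2%, so this is not a time to the trial's target.
- *8.2 min.* The endpoint is an expired-to-inspired ratio of 0.8. At a 2.5% dial, 0.8 × 2.5% = 2%, so the protocol equates it with the target. But Group C's dial is 3% and it needs only 2/3 = 0.667 of the dial setting, which is reached sooner. With a single exponential, the time becomes 8.2 × ln 3 / ln 5 = 8.2 × 1.0986 / 1.6094 = 5.60 min. The difference is then 8 − 5.60 = 2.40 min, with power 0.973.

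**The Introduction's time-constant rule.** With a reserve volume of 9–10 L, the time constant at 6 L/min is 9/6 = 1.5 to 10/6 = 1.67 min.

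- Three time constants are 4.5–5.0 min, so the difference from 8 min is 3.0–3.5 min and power is at least 0.998. That is the time to a 95% change, which is more than Group C needs.
- Filling to 2/3 of the dial takes ln 3 = 1.10 time constants, or 1.65–1.83 min. The same no-uptake model gives the over-pressure arm −ln(1 − 2/8) × 18 to 20 = 5.18–5.75 min. The difference is 3.53–3.92 min, with power above 0.999.

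These are rough and mutually inconsistent. The 8.2 min figure implies a time constant of 8.2/1.609 = 5.1 min, against 1.5–1.67 min from the volume rule. SD 2 would also exceed a Group C mean of 1.65–1.83 min. They cannot forecast Group C's time or bracket it. They do show that once the dial or the time-constant rule is considered, the difference comes out above 2 min.

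**What the trial can resolve.** The 95% confidence half-width is t(0.975, 42) × 2 × √(2/22) = 1.22 min at 22 per group, and 1.16 min at 24.

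**The case for a change.** The strongest case is that the nearest match in the Introduction shares Group C's 6 L/min flow, and its endpoint is one the protocol itself equates with 2% end-tidal sevoflurane. It took 8.2 min, almost the same as the 8 min assumed for the over-pressure arm. Power against a 0.2 min difference is 6%, and about 2,102 per group would be needed for 90%. A non-significant result might then be mistaken for similarity. The protocol chose to set out its derivation, so it could fairly be asked to complete it.

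Part of this stands: the protocol gives neither a Group C time nor a reason for 2 min. The rest does not carry. The comparison ignores the lower dial and the nitrous oxide. Low power against 0.2 min (12 seconds) is also no defect in a trial designed to detect 2 min. If the observed difference were −0.2 min with SD 2, the interval would run from −0.2 − 1.22 = −1.42 to −0.2 + 1.22 = 1.02 min, excluding a 2 min difference in either direction. At the other extreme, a true difference of 5 min would need only about 5 per group, so 22 would be ample. The protocol nowhere says that a P value will be read as proof of feasibility or similarity, and reporting an interval is ordinary practice commonly left to an analysis plan.

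**Conclusion.** No change is called for. The sample-size paragraph leaves out a rationale, but its stated inputs are complete and give the stated 22 per group. The 25% is correct against the one time assumed.

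The only low-power scenario (0.06) depends on a figure from a different dial and gas mixture, used unadjusted. The other scenarios examined give power of at least 0.97, so on these rough numbers 2 min is a cautious planning difference. This rests on a two-sided test, SD 2 in both arms, 8 min for the over-pressure arm and 22 analysed per group. Group C's true time remains unknown from the document.

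A sentence saying why 2 min is of interest, or what Group C was expected to take, would be a courtesy to readers. It would alter nothing in the number of patients, the procedures or the analysis.
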